4.2.1.3. Discontinuation

Treatment should be permanently discontinued for the following:

- Any Grade 2 drug-related uveitis or eye pain or blurred vision that does not respond to topical therapy and does not improve to Grade 1 severity within the re-treatment period OR requires systemic treatment
- Any Grade 3 non-skin, drug-related adverse event lasting > 7 days, with the following exceptions for drug-related laboratory abnormalities, uveitis, pneumonitis, bronchospasm, diarrhea, colitis, neurologic toxicity, hypersensitivity reactions, and infusion reactions:
- Grade 3 drug-related uveitis, pneumonitis, bronchospasm, diarrhea, colitis, neurologic toxicity, hypersensitivity reaction, or infusion reaction of any duration requires discontinuation

Grade 3 drug-related laboratory abnormalities do not require treatment discontinuation except:

- Grade 3 drug-related thrombocytopenia > 7 days or associated with bleeding requires Discontinuation
- Any drug-related liver function test (LFT) abnormality that meets the following criteria require discontinuation:
 - AST or ALT > 8 x ULN
 - Total bilirubin > 5 x ULN

-
- Concurrent AST or ALT > 3 x ULN and total bilirubin > 2 x ULN
 - Any Grade 4 drug-related adverse event or laboratory abnormality, except for the following events which do not require discontinued.
 - Isolated Grade 4 amylase or lipase abnormalities that are not associated with symptoms or clinical manifestations of pancreatitis. It is recommended to consult with the BMS Medical Monitor for grade 4 amylase or lipase abnormalities.
 - Isolated Grade 4 electrolyte imbalances/abnormalities that are not associated with clinical sequelae and are corrected with supplementation/appropriate management within 72 hours of their onset
 - Dosing interruptions to allow for prolonged steroid tapers to manage drug-related adverse events are allowed. Prior to re-initiating treatment in a subject with a dosing interruption lasting > 6 weeks, the BMS medical monitor must be consulted. Tumor assessments should continue as per protocol even if dosing is interrupted.
 - Dosing interruptions > 6 weeks that occur for non-drug-related reasons may be allowed if approved by the BMS medical monitor. Prior to re-initiating treatment in a subject with a dosing interruption lasting > 6 weeks, the BMS medical monitor must be consulted. Tumor assessments should continue as per protocol even if dosing is interrupted.

Any adverse event, laboratory abnormality, or intercurrent illness which, in the judgment of the Investigator, presents a substantial clinical risk to the subject with continued NIVOLUMAB or NIVOLUMAB and ipilimumab dosing.

4.2.1.4. Dose Adjustments, Dose Delays, and Missed Doses

There will be no dose adjustments allowed except if there has been $\pm 10\%$ weight change since the previous treatment (cycle 1) visit. There will be no dose adjustments for ipilimumab. Starting 4 weeks after the last co-administered dose in cycle 1, subjects will be administered a flat dose 480 mg NIVOLUMAB IV every 4 weeks (Q4W) in cycles 2-5 and there will be no dose adjustments for weight.

During the Induction Treatment Period (cycle 1) and Treatment/Follow-up periods (cycles 2-5), if there is a dose delay between 1 and 7 days, the procedures at the original scheduled visit should be performed as soon as possible. If the delay is more than 7 days, the visit and dose will be considered missed; the procedures at the next scheduled visit should be performed, and subsequent visits will follow every 2 weeks. Subjects with infusion delays > 35 days (ie, 2 missed doses + 7 days) should discontinue the study drugs and complete the remaining study visits (without dosing).

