Nivolumab ^{2,11}		•	•	•	•	• ¹³	•	•	•	•	•	•	•				

Key: CT = computed tomography, HIV = human immunodeficiency virus; ECOG = Eastern Cooperative Oncology Group; MRI = magnetic resonance imaging

FOOTNOTES:

- ¹Every effort should be made to infuse NIVOLUMAB in a 60-minute timeframe.
- ² The NIVOLUMAB dosage may be adjusted if there is a ± 10% weight change since the previous weight measurement only during cycle 1 Induction Treatment. No dose escalations or de-escalations are allowed during cycles 2-5 due to the use of flat dosing of NIVOLUMAB at 480 mg every 4 weeks. No dose escalations or de-escalations are allowed during cycles 2-5 due to the use of flat dosing of NIVOLUMAB at 480 mg every 4 weeks.
- ³ Informed consent must be signed before initiation of any study drug treatment or procedure. It may be signed more than 28 days before the first dose.
- ⁴ Pregnancy testing must be performed before any study drug is administered. The test result must be negative for a subject to receive study drug(s).
- ⁵ Vital signs will be monitored immediately prior to the NIVOLUMAB infusion; every 15 minutes during the 30 or 60-minute NIVOLUMAB infusion; and 15 and 30 minutes after completion of the NIVOLUMAB infusion. When slowing or re-starting the NIVOLUMAB infusion due to an infusion reaction/adverse event, vital signs should be monitored every 15 minutes or as directed by the Investigator until the infusion is completed, and 15 and 30 minutes after completion of the infusion and/or the subject is stabilized.
- ⁶ These evaluations are for baseline reference; subsequent evaluations may be performed if clinically indicated.

-
- ⁷ Sample to be drawn/collected pre-treatment at visits where 1 or more study drug will be administered. Hematology and serum chemistries for Cycle 1 Day 1 will not be re-drawn if screening labs were completed within 72 hours prior to study drug administration. This treatment group will draw amylase and lipase also.
- ⁸ CT neck will be done only in patients with prior disease in the head and neck
- ⁹ In patients who have not had disease progression, re-imaging should be performed every 6-12 months (minimum of every 12 months) for the first 2 years, then every 12 months (at the discretion of the treating physician) indefinitely or until progression.

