- ¹⁰ Survival statuses for all patients who have discontinued from study treatment will be collected every 6 months (+/- 1 month) until death, lost to follow-up, or withdrawal of consent for survival follow-up. Follow-up contact may be done in person at the study center or by telephone; survival information may be obtained from family members or other medical professionals caring for the patient. Survival information including post-study treatment modalities and date and site of disease progression will be documented in the source documents and survival eCRF. Social security death index (SSDI) and other public records will be used if necessary to confirm survival status and/or date of death.
- ¹¹ There is only one 12 week induction treatment cycle (cycle 1). The ipilimumab will be at 1 mg/kg every 3 weeks for 4 doses during the 12 week induction cycle, and NIVOLUMAB will be at 3 mg/kg every 3 weeks for 4 doses during the 12 week induction treatment cycle then at 480mg every 4 weeks for 48 weeks during cycles 2-5.
- ¹² To be obtained every 12 weeks. Patients that discontinue therapy for any reason will only have the immunology procedures collected at the next mandated protocol timepoint, but not thereafter.
- ¹³ Radiology exams will be completed prior to dosing at week 12 and every 12 weeks prior to each dosing visit.
- ¹⁴ Tissue will be submitted, if available, as outlined in section 5.6.1
- ¹⁵ Tissue from any post-relapse biopsy will be requested for analysis by immunohistochemistry as outlined in section 5.6.1.

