3.4.6 Early Discontinuation Criteria and Procedures

3.4.6.1 Discontinuation of Study Drug

It is the right and duty of the Investigator to discontinue the study drugs of any subject if he feels that discontinuation of the study drugs is necessary to protect the subject, or that there are unmanageable factors that may interfere significantly with the study procedures and/or the interpretation of results.

Administration of the study drugs will be discontinued if the subject develops a DLT, documented relapse, or other intolerability to the study drugs.

Administration of the study drugs may be discontinued during the study for any of the following reasons:

- Adverse event(s)
- Protocol violation
- Subject withdrew consent
- Lost to follow-up
- Other
- Death

For subjects who discontinue the study drugs for any reason, the remaining study visits and associated evaluations (without dosing) should be completed. Patients who discontinue the study drug(s) due to a toxicity will be followed until the toxicity resolves to baseline. Patients will continue to be followed on the protocol schedule for radiology assessments and for relapse free survival. Pharmacokinetic samples will only be collected at the visit following study drug discontinuation.

All subjects will be followed for adverse events for at least 70 days after the last dose of study drugs and for survival follow-up indefinitely until withdrawal of consent or death.

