Because of the potential for clinically meaningful nivolumab or ipilimumab related AEs requiring early recognition and prompt intervention, management algorithms have been developed for suspected pulmonary toxicity, GI, hepatotoxicity, endocrinopathy, skin toxicity, neurological toxicity and nephrotoxicity. For the overlapping adverse event management algorithms present in both the NIVOLUMAB and ipilimumab IB (**GI, hepatic, and endocrine** algorithms), the recommendations are to follow the NIVOLUMAB IB adverse event algorithms as opposed to the ipilimumab IB algorithms.

Subjects may resume treatment with study drug (s) when the drug-related AE(s) resolve to Grade 1 or baseline value, with the following exceptions:

- Subjects may resume treatment in the presence of Grade 2 fatigue

-
- Subjects who have not experienced a Grade 3 drug-related skin AE may resume treatment in the presence of Grade 2 or less skin toxicity
 - Subjects with baseline Grade 1 AST/ALT or total bilirubin who require dose delays for reasons other than a 2-grade shift in AST/ALT or total bilirubin may resume treatment in the presence of Grade 2 AST/ALT OR total bilirubin
 - Subjects with combined Grade 2 AST/ALT AND total bilirubin values meeting discontinuation parameters should have treatment permanently discontinued
 - Drug-related pulmonary toxicity, diarrhea, or colitis, must have resolved to baseline before treatment is resumed
 - Drug-related endocrinopathies adequately controlled with only physiologic hormone replacement may resume treatment

If the criteria to resume treatment is met, the subject should restart treatment at the next scheduled timepoint per protocol. However, if the treatment is delayed past the next scheduled timepoint per protocol, the next scheduled timepoint will be delayed until dosing resumes. If treatment is delayed greater than 6 weeks, the subject must be permanently discontinued from study treatment, except as specified in the discontinuation section below.

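### Section 4.2.1.4 cancels the visit along with the dose after a delay of more than 7 days, so scheduled safety tests and immune blood are not made up, in conflict with sections 4.2.1.2 and 4.2.1.3

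*Combined protocol and SAP*

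**What the plan says.** Section 4.2.1.4 separates short from long delays. For a short one, "if there is a dose delay between 1 and 7 days, the procedures at the original scheduled visit should be performed as soon as possible". For a longer one: "If the delay is more than 7 days, the visit and dose will be considered missed; the procedures at the next scheduled visit" are then to be done. The same paragraph takes patients delayed more than 35 days off drug but has them complete the remaining visits without dosing.

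Two neighbouring sections give other rules for a patient on hold:

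- Section 4.2.1.2: "if the treatment is delayed past the next scheduled timepoint per protocol, the next scheduled timepoint will be delayed until dosing resumes".
- Section 4.2.1.3, stated twice: "Tumor assessments should continue as per protocol even if dosing is interrupted".

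For patients who stop drug, section 3.4.6.1 says: "For subjects who discontinue the study drugs for any reason, the remaining study visits and associated evaluations (without dosing) should be completed". Two passages qualify this. Table 1 footnote 12 limits their immune sampling to one further timepoint, and section 4.2.4.1 makes the 12-weekly scans after a toxicity stop wait until the toxicity has resolved.

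Table 1 links assessments to dosing. Footnote 7: "Sample to be drawn/collected pre-treatment at visits where 1 or more study drug will be administered". Footnote 13: "Radiology exams will be completed prior to dosing at week 12 and every 12 weeks prior to each dosing visit".

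**The concern.** A held patient is still in follow-up and can be assessed. Read literally, 4.2.1.4 nevertheless removes the visit. A hold of 8 to 35 days therefore costs a visit, while a longer one, which ends treatment, keeps the later visits.

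The loss would not be random. Section 4.2.1.2 delays dosing for most drug-related non-skin events of Grade 2 or higher. Section 4.6.1 requires steroids given for immune-related events to be back at a non-immunosuppressive dose for at least 2 weeks before the next dose. The assessments dropped would come mostly from patients with toxicity. Safety is the primary objective and immune response a secondary one. Section 5.6.3 reports a percentage of responders without saying how absent samples are handled, and the only worked example in section 6.4 is a missing adverse event date.

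**Working it through.** The plan gives no figure to reproduce. The check compares the passages and applies calendar arithmetic to the stated schedule: cycle 1 visits on Days 1, 22, 43, 64 and 78 (Table 1), then dosing every 4 weeks for 48 weeks, with scans every 12 weeks.

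**1. What each rule does to the visit of a patient on hold**

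| Situation | Source | Visit's assessments |
|---|---|---|
| Delay of 1 to 7 days | 4.2.1.4 | Made up |
| Delay over 7 days | 4.2.1.4 | Visit missed; next visit's procedures follow |
| Delay past the next timepoint | 4.2.1.2 | Timepoint postponed |
| Dosing interrupted | 4.2.1.3 | Tumor assessments continue |
| Delay over 35 days, or drug stopped | 4.2.1.4, 3.4.6.1 | Remaining visits done without dosing |

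The second, third and fourth rows can apply to the same patient and cannot all be followed.

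**2. Whether a toxicity hold passes 7 days.** Section 4.6.1 requires at least 14 days at the lower steroid dose. If a dose falls due while an event is being treated with immunosuppressive steroids, the delay normally exceeds 7 days.

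**3. Gap left by one cancelled visit**, if the next visit keeps its calendar date:

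- Day 22 missed: 43 − 1 = 42 days.
- Day 43 missed: 64 − 22 = 42 days.
- Day 64 missed: 78 − 43 = 35 days.
- 4-weekly phase: 2 × 28 = 56 days.

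**4. What falls in the gap**

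- *Safety.* Section 5.1.1 schedules a physical examination at all visits, and 5.1.6 schedules laboratory samples by Table 1. Nothing reinstates these at a cancelled visit.
- *Immune blood.* Footnote 7 links sampling to dosing visits, and no passage restores a held patient's sample. Sections 5.6.3 and 6.3.4 name Week 7, which Table 1 places on Day 43, a dosing visit. Section 6.3.4 also names Week 13, section 6.3.4.1 names Week 12, and Appendix 4 names Weeks 5, 9 and 12. With such varied timepoints, the number of samples at risk cannot be counted.
- *Scans.* No cycle 1 dosing visit carries a scan. If flat dosing starts at Week 12, as Table 1 appears to show, the dosing weeks are 12, 16, ..., 56, and scan weeks 12, 24, 36 and 48 fall on 4 of 12 dosing visits. If it starts 4 weeks after the last combination dose (Day 64 + 28 = Day 92, in Week 14), the dosing weeks are 14, 18, ..., 58 and none of the 12 is a scan week. Only if a scan were dropped and left to the next scan timepoint would the interval grow from 12 × 7 = 84 to 24 × 7 = 168 days.

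**5. Whether the paragraph fits this trial's schedule.** It explains 35 days as two missed doses plus 7 days and sends later visits to a 2-weekly rhythm. Two missed doses plus 7 days is 2 × 14 + 7 = 35 at 2-week dosing, 2 × 21 + 7 = 49 at 3-week dosing and 2 × 28 + 7 = 63 at 4-week dosing. Only the first matches, and this trial doses every 3 and then every 4 weeks. The 35-day limit also differs from the 6-week (42-day) limit in 4.2.1.2.

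**The case against.** The strongest reply is that other provisions cover most of what matters, and much of that stands.

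- A reader might infer that held patients' scans are skipped and relapse is dated up to 12 weeks late. The documents do not support this as a certainty. Section 4.2.1.3 is the provision specific to imaging and keeps it. The Synopsis and section 2.1 allow maintenance only for patients without relapse at Week 12, so that scan is a condition for going on. What remains is a conflict of rules.
- A reader might infer that the Week 12 immune sample is lost. Appendix 4 separates that sample, a follow-up pheresis, from the infusion-day draws. Footnote 7 can also be read as fixing the order of draw and dose, not as making the draw depend on a dose. Earlier draws at dosing visits remain exposed under 4.2.1.4.
- A reader might infer that patients who stop for good lose nothing. Footnote 12 and section 4.2.4.1 limit their immune sampling and scans. The contrast holds for visits, not for every assessment.
- Safety follow-up does not cease. Laboratory tests are required in the 72 hours before each further dose (5.1.6), adverse events are collected continuously (6.8), and drug-related diarrhea or colitis of Grade 2 or higher needs at least weekly visits (6.10). But tests before re-dosing do not replace the panel due during the hold, and the weekly visits cover one type of event.
- The rule covers any delay over 7 days, not only toxicity. That is so; toxicity is the foreseeable cause, not the only one.

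**Conclusion.** The text is wrong as written and should be corrected. Followed literally, 4.2.1.4 drops scheduled safety assessments, and any immune blood due, in patients who remain in follow-up. It also contradicts 4.2.1.2 and 4.2.1.3. The gap between attended visits would be 35 to 42 days in cycle 1 and 56 days later, assuming one cancelled visit and a next visit on its calendar date. With 20 patients, each patient without an assessment is 1/20 = 5% of the planned sample at that timepoint.

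How many assessments would be lost, and in which direction results would shift, cannot be derived. A reader might take the predecessor cohorts in section 1.4.3 as hold rates: 3 of 20 did not continue past 12 weeks in one, and toxicity kept 10 of 20 from finishing 12 weeks in the other. Those figures describe not completing or not continuing, not temporary holds, and the second cohort had a different regimen. The documents also say nothing about how immune response differs between held and other patients. No bias estimate is therefore offered.

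**What to change.** In 4.2.1.4, limit the word *missed* to the dose and add a sentence such as:

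> A held or missed dose does not cancel the other assessments of that visit. Imaging, safety laboratory tests, adverse event review and immune blood stay on the original calendar, within the visit window.

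State that immune blood may then be taken by peripheral draw instead of pheresis, which the Synopsis (Immunology) and section 5.3 already allow. Cross-refer 4.2.1.2, 4.2.1.3 and Table 1 footnotes 7, 12 and 13 to this sentence, so that the footnote limiting immune sampling after discontinuation is not applied to patients on hold.

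The sponsor must also reconcile the dose-timing text in these sections: the 2-weekly rhythm and 35-day limit in 4.2.1.4 against 3- and 4-week dosing and the 6-week limit in 4.2.1.2. No dosing rule is proposed here.

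The cost is a written amendment (section 12.2) and some visits without dosing, which the plan already requires for patients who have stopped drug. The assessments themselves are already scheduled.

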i.v.	intravenous, intravenously
ICF	informed consent form
ICH	International Conference on Harmonisation
IL-2	interleukin-2
INF	Interferon
irAE	Immune-related adverse event
IRB	Institutional Review Board
irCR	Immune-related complete response
irPD	Immune-related progressive disease
irPR	Immune-related partial response

Abbreviation	Term
irRC	Immune-related Response Criteria
irSD	Immune-related stable disease
mAb	monoclonal antibody
NIVOLUMAB	PD-1-specific, fully human IgG4 mAb
MedDRA	Medical Dictionary for Regulatory Activities
mWHO	Modified World Health Organization
MPR	Mixed Lymphocyte Reaction
MTD	maximum tolerated dose
NCI	National Cancer Institute
PBMC	peripheral blood mononuclear cells
PCC	Perlmutter Cancer Center
PD-1	Programmed Death-1
PD-L1	Programmed Death-Ligand 1
PI	Propidium Iodide
PR	Partial Response
PVG	Pharmacovigilance
SAE	serious adverse event
RECIST	Response Evaluation Criteria in Solid Tumors
SOC	system/organ/class
SOP	standard operating procedure
SPD	Sum of Product Diameters
SSAE	Serious or Significant Adverse Event
TEAE	treatment-emergent adverse event
TNF	tumor necrosis factor
ULN	upper limit of normal
URTI	upper respiratory tract infection
US	United States of America
UTI	urinary tract infection
WBC	white blood cell
WHO	World Health Organization

TABLE 1: TIME AND EVENTS SCHEDULE

Examination	Screening	Cycle 1 Treatment Period ^{11, 13} (Visits must occur ± 7 days of the scheduled visit)					Cycle 2-5 Treatment Period ^{11, 13} (Visits must occur ± 7 days of scheduled visit; Every 4 weeks for 48 weeks)						Study Completion/ Early Withdrawal (Visit to occur 12 week ± week after last dose)	Survival Follow-up	
		2	3	4	5	6	7	8	9	10	11	12			
Visit	1	2	3	4	5	6	7	8	9	10	11	12			
Week	-1	1	4	7	10	12									
Timepoint (Day)	-28 to -1	1	22	43	64	78									
Research Procedures															
• Sample for immunogenicity ⁷		•			•							•	• 1 3	•	
• Serum for cytokine panel ⁷		•			•							•	• 1 3	•	
• Cellular immune assays ⁷		•			•							•	• 1 3	•	
• Cryopreserved serum ⁷		•			•							•	• 1 3	•	
• Tissue Submission ¹ 4		•	• ¹⁵	• ¹⁵	• ¹⁵	• ¹⁵	• ¹⁵	• ¹⁵	• 1 5		• ¹⁵				

Efficacy Procedures																	
CT/MRI (neck, chest, abdomen, pelvis) ^{9, 12}	•					•	•						•	•			
							1							1			
							4							4			
															•		•
CT/MRI (Brain)	•					•	•						•	•			
							1							1			
							4							4			•
Follow-up contact ¹⁰																	•
Study Drug Administration																	
Ipilimumab ¹¹		•	•	•	•												

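### The missed-dose rule in section 4.2.1.4 fits neither dosing phase and conflicts with the delay rules in sections 4.2.1.2 and 4.2.1.3

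*Combined protocol and SAP*

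**What the plan says.** Dosing is 3-weekly in cycle 1 (Days 1, 22, 43 and 64) and 4-weekly in cycles 2-5 (Table 1 and its footnote 11). Table 1 gives both phases a 7-day window either side: "Visits must occur ± 7 days of the scheduled visit" for cycle 1 and "Visits must occur ± 7 days of scheduled visit; Every 4 weeks for 48 weeks" for cycles 2-5.

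Three sections then govern late doses.

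- **Section 4.2.1.4** expressly covers both phases. A dose 1 to 7 days late is given as soon as possible. Beyond that, "If the delay is more than 7 days, the visit and dose will be considered missed", the patient moves to the next scheduled visit, and "subsequent visits will follow every 2 weeks. Subjects with infusion delays > 35 days (ie, 2 missed doses + 7 days) should discontinue" study drug. It names no exception.
- **Section 4.2.1.2** restarts treatment at the next scheduled timepoint, but "if the treatment is delayed past the next scheduled timepoint per protocol, the next scheduled timepoint will be delayed until dosing resumes". Its limit is longer: "If treatment is delayed greater than 6 weeks, the subject must be permanently discontinued from study treatment", subject to the discontinuation section.
- **Section 4.2.1.3** supplies the exceptions: "Dosing interruptions to allow for prolonged steroid tapers to manage drug-related adverse events are allowed", and "Dosing interruptions > 6 weeks that occur for non-drug-related reasons may be allowed if approved by the BMS medical monitor". For re-initiation after more than 6 weeks, the medical monitor must be consulted.

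**The concern.** These rules decide whether a patient with a delayed infusion is dosed again, and on which day. If two sections give different answers, the choice of section decides who is recorded as having discontinued. Safety and tolerability are the primary objective. Section 1.4.3 describes the predecessor cohort on the same induction doses by the number continuing past the 12-week combination period (17 of 20), so a discontinuation count is a natural result to report here.

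Long delays are foreseeable. Section 4.6.1 requires steroids given for infusion reactions or irAEs to be at 10 mg/day prednisone equivalent or less for at least 2 weeks before the next dose.

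**Working it through.** **Inputs.** Dosing interval 21 days in cycle 1 and 28 days in cycles 2-5; visit window ±7 days (Table 1). Section 4.2.1.4: a dose is missed once more than 7 days late; stop beyond 35 days. Section 4.2.1.2: stop beyond 6 weeks = 6 × 7 = 42 days. Assumption: delay runs from the scheduled date of the first missed dose, since the sections do not define the starting point.

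**Reproducing the 35 days.** The section explains its limit as two missed doses plus 7 days. This can be counted in two ways.

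| Schedule | Two intervals + 7 | Day the second dose becomes missed (one interval + 7) |
|---|---|---|
| 2-weekly | 2 × 14 + 7 = 35 | 14 + 7 = 21 |
| 3-weekly (cycle 1) | 2 × 21 + 7 = 49 | 21 + 7 = 28 |
| 4-weekly (cycles 2-5) | 2 × 28 + 7 = 63 | 28 + 7 = 35 |

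The first count gives 35 only for 2-weekly dosing and the second only for 4-weekly dosing. Neither gives 35 for cycle 1.

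**Visit interval.** Fourteen days lies outside the 4-weekly window (28 ± 7 = 21 to 35) and at the extreme edge of the 3-weekly window (21 ± 7 = 14 to 28).

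**Limit, cycle 1.** Suppose the Day 22 and Day 43 doses are missed. The Day 64 visit may fall on Days 57-71 (64 ± 7), which is 35 to 49 days after Day 22.

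- Day 57 (35 days): both sections allow dosing.
- Days 58-64 (36-42 days): 4.2.1.4 says stop; 4.2.1.2 allows resumption. The nominal Day 64 visit, at 64 − 22 = 42 days, is in this range.
- Days 65-71 (43-49 days): beyond both limits, unless a 4.2.1.3 exception applies.

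**Limit, cycles 2-5, dosing at scheduled slots.** One missed dose gives 28 ± 7 = 21 to 35 days, which both sections allow. Two give 56 ± 7 = 49 to 63 days, beyond both limits; a 4.2.1.3 exception could still permit dosing, and 4.2.1.4 does not acknowledge it. The 36-42 day conflict arises here only if the timepoint is shifted under 4.2.1.2.

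**Rescheduling, cycle 1.** Suppose the Day 22 dose is missed and the criteria to resume are first met on one of Days 51-56, that is, after Day 43 + 7 = 50 and before Day 64 − 7 = 57.

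- Under 4.2.1.2, on its plain reading, the Day 43 timepoint has been held and can be dosed at once. The delay is 51 − 22 = 29 to 56 − 22 = 34 days, inside both limits.
- Under 4.2.1.4, the Day 43 dose is already missed and the patient goes to the Day 64 visit. Dosing there on Day 58 or later passes that section's own 35-day limit.

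**Effect on a reported rate.** One patient handled differently is 1/20 = 5 percentage points, or 1/25 = 4 points if all 25 permitted subjects are treated.

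**The case against.** - **The 35 days can be read correctly for cycles 2-5.** Using the section's own definition of a missed dose, the second 4-weekly dose becomes missed after day 35. Those cycles hold 48/4 = 12 of up to 16 nivolumab doses. This stands, but the rule also covers cycle 1, where neither count works. That the text was carried over from a 2-weekly design is only an inference, and the conflict does not depend on it.
- **Section 4.2.1.1 already limits skipped doses.** After a Grade 3 irAE that is not a DLT, therapy may continue only if no more than one dose was skipped, so the two-missed-dose example does not decide redosing for those patients. This stands. It does not cover non-drug-related delays. For selected Grade 2 irAEs the section speaks of skipping one dose but sets no stopping limit.
- **The exceptions may be reconcilable.** Section 4.2.1.2 defers to 4.2.1.3, and 4.2.1.4 says only that subjects should discontinue, where 4.2.1.2 says must. A reader could let the specific exceptions prevail beyond 42 days. That does not help at 36-42 days, where 4.2.1.4 stops patients whom 4.2.1.2 would not. Always applying the stricter rule would make the 6-week limit and its exceptions pointless.
- **The rescheduling rules partly agree.** Both start from the next scheduled visit and part only when the delay runs past it; the illustrated gap is six days. This limits the size of that part but does not remove it.
- **The statistical effect is thin.** No discontinuation rate is prespecified in section 6.3.3; section 5.5 only records completion and the reason for withdrawal. This is fair, and it is why the point is not rated higher.

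**Conclusion.** The concern holds and should be fixed. The 2-week visit interval fits neither phase. The 35-day stop contradicts the 6-week limit for delays of 36-42 days, chiefly in cycle 1, and omits the 4.2.1.3 exceptions. The rescheduling rules diverge once a delay passes the next timepoint. No other section reconciles them.

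The day ranges rest on counting delay from the first missed dose and on the Table 1 windows. How many patients would be affected cannot be derived from the documents; each would move a discontinuation rate by about 4 to 5 percentage points. The DLT count and the DLT stopping rule are unaffected.

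**What to change.** 1. **Visit interval (4.2.1.4).** Replace the 2-week interval with 3 weeks in cycle 1 and 4 weeks in cycles 2-5.
2. **Limit (4.2.1.4).** Replace the 35-day limit and its explanation with: more than 6 weeks after the scheduled date of the first missed dose, except as specified in 4.2.1.3. If the sponsor prefers another value, use it in both 4.2.1.2 and 4.2.1.4.
3. **Rescheduling (4.2.1.2 and 4.2.1.4).** Use one rule in both sections. Suggested: a dose not given within 7 days of its scheduled date is missed, and dosing resumes at the next scheduled timepoint (±7 days) once the criteria to resume are met. Then delete the 4.2.1.2 sentence that holds the timepoint until dosing resumes. If the sponsor prefers the shifting timepoint, delete the missed-dose sentence in 4.2.1.4 instead.

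The one-skip condition in 4.2.1.1 for Grade 3 irAEs that are not DLTs stays in force. As an optional clarification, 4.2.1.1 could state that the 4.2.1.3 discontinuation list takes precedence for Grade 3 irAEs.

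The cost is amendment wording only, with no extra patients, visits or procedures.
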